### 19.1. ADVERSE EVENTS

AEs will be coded using Medical Dictionary for Regulatory Activities (MedDRA) central coding dictionary, Version 23.0 or higher. Treatment-emergent adverse events (TEAEs) are defined as:

- An AE that occurs after the first dose of study treatment (olorinab or placebo) that was not present before the first dose of treatment, OR
- An AE that increases in severity after the first dose of study treatment (olorinab or placebo), if the event was present before the first dose of treatment.

All TEAEs will be coded and summarized by system organ class (SOC) and preferred term (PT) and will be presented by descending order of frequency. AEs occurring before the first dose of study treatment will be summarized separately. Listings will include all AEs (TEAEs and Non-TEAEs).

See Appendix 2. Partial Date Conventions for handling of partial dates for AEs for the purpose of assigning treatment-emergent flags. In the case where it is not possible to define an AE as treatment-emergent or not, the AE will be classified by the worst case; i.e. treatment emergent.

#### **19.1.1. ALL TEAES**

All TEAEs will be summarized by SOC and PT in each treatment and with olorinab 25 and 50 mg pooled and olorinab active treatments pooled and presented by descending order of

frequency in any treatment. TEAEs will also be summarized by maximum severity and relationship to study treatment. A separate summary of related TEAEs and related TEAEs by maximum severity will also be provided.

### **19.1.2. SEVERITY**

Severity is classified by grade using the Common Terminology Criteria for Adverse Events version 5.0 (CTCAE v5.0) system as defined below. The CTCAE grade will be assessed by a nurse and/or physician and will be recorded in the AE severity Section on the Adverse Events eCRF.

**Grade 1:** Mild; asymptomatic or mild symptoms; clinical or diagnostic observations only; intervention not indicated.

**Grade 2:** Moderate; minimal, local or noninvasive intervention indicated; limiting age-appropriate instrumental activities of daily living.

**Grade 3:** Severe or medically significant but not immediately life-threatening; hospitalization or prolongation of hospitalization indicated; disabling, limiting self-care activities of daily living (e.g., preparing meals, shopping

for groceries or clothes, using the telephone, managing money).

**Grade 4:** Life-threatening consequences, urgent intervention indicated.

**Grade 5:** Death related to AE.

TEAEs with a missing severity but identified as a life-threatening serious adverse event (SAE) or one requiring initial or prolonged hospitalization will be classified as Grade 4 (Potentially Life-threatening), otherwise missing severity will be classified as Grade 3 (severe). If a subject reports a TEAE more than once within that SOC/ PT, the AE with the greatest severity will be used in the corresponding severity summaries.

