#### 9.3. MISSING DATA

Missing safety data will generally not be imputed, with the exceptions of AE relationship to study treatment (as described in Section 19.1.3), partial or missing AE start dates, and Concomitant Medication (CM) start dates. Details about date imputations are described in Appendix 2. Partial Date Conventions. No other missing safety data will be imputed.

Missing efficacy data will be handled as described in Sections 18.1.2, 18.2.2, and 18.3.21 of this analysis plan. Sensitivity analyses will be conducted to assess the robustness of the

primary and secondary endpoint results, as described in Sections 18.1.4 and 18.2.4, respectively. Missing PK data will be handled as described in Section 20.2 of this analysis plan.

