#### 19.1.7. TEAES LEADING TO DEATH

TEAEs leading to Death are those events which are recorded as "Fatal" on the Adverse Events page of the eCRF. A summary of TEAEs leading to death by SOC and PT will be prepared by treatment.

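### The missing-severity rule in both SAPs has no branch for fatal events, so a death with no grade is reported as Grade 3 or 4 and never Grade 5; the missing-data sections also say severity is not imputed

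*SAP*

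**What the plan says.** Main Study SAP 19.1.2 prints the CTCAE v5.0 scale and then a rule for TEAEs with no recorded severity.

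- **Scale.** Grade 4 is "Life-threatening consequences, urgent intervention indicated". Grade 5 is "Death related to AE".
- **Rule, first branch.** A life-threatening SAE "or one requiring initial or prolonged hospitalization will be classified as Grade 4 (Potentially Life-threatening").
- **Rule, remainder.** "otherwise missing severity will be classified as Grade 3 (severe").

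SAP 9.3 covers missing safety data in general. It names three exceptions to non-imputation (AE relationship, partial or missing AE start dates, and concomitant-medication start dates) and then says: "No other missing safety data will be imputed".

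A fatal outcome is available as a data item. In SAP 19.1.7, "TEAEs leading to Death are those events which are recorded as" fatal on the AE page of the eCRF. Protocol 7.8.1.2 lists fatal as an SAE criterion in its own right, apart from life-threatening and hospitalisation.

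The LTE SAP repeats the scale and rule in 18.1.2, the closed list in 8.3 and the fatal-outcome definition in 18.1.7.

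**The concern.** The rule can return only Grade 3 or Grade 4, while the scale above it has a grade for death. Applied as written, a fatal TEAE with a blank grade is placed below the grade that the same section defines for it. The fatal-TEAE table would then count a death that the Grade 5 row of the severity table does not.

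The second problem is a contradiction. A programmer working from 9.3 would leave severity blank; one working from 19.1.2 would fill it in. The two produce different tables.

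Adverse events are listed under the primary endpoints for the Main Study (Protocol 8.3.1.1) and for the LTE (Protocol Synopsis). Maximum-severity summaries are planned for all TEAEs and for related TEAEs (SAP 19.1.1 and 19.1.9; LTE SAP 18.1.1 and 18.1.9). The LTE overview in 18.1.9 keeps the severity rows but, unlike SAP 19.1.9, has no line for TEAEs leading to death. Within that one LTE table, the severity rows are the only place where a death would show as a death.

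**Working it through.** The plan states no figure to reproduce, because this is a classification rule. The check applies the rule to every combination of the three relevant flags.

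**Inputs.** Severity is missing. The flags are fatal (Protocol 7.8.1.2; SAP 19.1.7), life-threatening and hospitalised (both used in the SAP 19.1.2 rule).

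**Rule.** Grade = 4 if life-threatening or hospitalised; otherwise 3. The fatal flag does not enter.

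**Scale.** Fatal gives 5. Not fatal but life-threatening gives 4. For the other two rows the scale does not settle the grade.

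| Fatal | Life-threatening | Hospitalised | Grade by rule | Grade by printed scale |
|---|---|---|---|---|
| yes | no | no | 3 | 5 |
| yes | no | yes | 4 | 5 |
| yes | yes | no | 4 | 5 |
| yes | yes | yes | 4 | 5 |
| no | yes | no | 4 | 4 |
| no | yes | yes | 4 | 4 |
| no | no | yes | 4 | not determined |
| no | no | no | 3 | not determined |

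The rule conflicts with the scale in all four fatal rows: by 5 − 3 = 2 grades in one and by 5 − 4 = 1 grade in three. A death flagged only as fatal (Grade 3) ranks below a non-fatal hospitalised event (Grade 4).

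**Size of one case.** SAP section 8 plans 60 subjects per arm, so one subject is 1/60 = 1.7% of a Main Study arm. LTE enrolment is uncapped, so there is no corresponding planned denominator.

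**Missing-data sections.** Severity is not among the three exceptions in SAP 9.3 or LTE SAP 8.3. SAP 19.1.2 and LTE SAP 18.1.2 impute it. As worded, both statements cannot hold.

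**The case against.** **The trigger is remote.** Protocol 7.8.1.5 requires maximum severity to be recorded with the outcome. Protocol 7.8.2.2 makes severity an AE eCRF item, and 7.8.2.5 puts SAEs into the database within 24 hours of awareness. SAP 5.2 places the final analysis after queries are closed. A death with a blank grade would have to survive all of this. That stands, and it limits how often the rule would matter. It does not make the rule right when it is used.

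**No death would be hidden.** A reader might infer that a death could drop out of the safety report. The documents do not support that: fatal TEAEs have their own summary and deaths have a listing, neither of which depends on grade (SAP 19.1.7 and 19.2; LTE SAP 18.1.7 and 18.2). SAP section 19 also plans no statistical comparison of safety data unless otherwise specified.

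**Section 9.3 is a loose overview.** It mentions only start dates, yet Appendix 2 also imputes stop dates, and 19.1.2 is explicit enough to program from. So the conflict is editorial, but the closing sentence of 9.3 is categorical and should be corrected.

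**Hospitalised, non-fatal events.** A reader might go further and say the rule also over-grades a hospitalised event that is not life-threatening, because the Grade 3 definition includes "hospitalization or prolongation of hospitalization indicated". The documents do not support this. The true grade is unknown, and the scale does not say that every hospitalised event is Grade 3. Grade 4 also covers a need for urgent intervention. Rounding up matches the neighbouring conventions: unclear treatment emergence takes the worst case (SAP 19.1) and missing relationship counts as related (SAP 19.1.3). Moving these events to Grade 3 would be less conservative and would put them level with any non-serious TEAE lacking a grade.

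**Conclusion.** The point holds for fatal events and for the contradiction between sections. With severity missing, no fatal TEAE can reach Grade 5 under either SAP. It becomes Grade 3 when neither other flag is set and Grade 4 in the remaining three combinations, so it would be wrong to say that every such death becomes Grade 3. The worst-case convention cannot justify this, because here the rule moves the event down.

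This is a minor correction. It affects only the severity summaries, and only when a fatal TEAE has no grade at analysis. That this is rare is an assumption drawn from the data-collection safeguards; the documents give no rate of missing severity and no expected number of deaths.

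**What to change.** In SAP 19.1.2 and LTE SAP 18.1.2, put a new branch first: when severity is missing and the AE outcome is recorded as fatal, assign Grade 5. Leave the Grade 4 and Grade 3 branches as they are. In SAP 9.3 and LTE SAP 8.3, add AE severity to the listed exceptions, with a reference to the severity section.

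The cost is one sentence and one list item in each SAP, and one line of derivation using a field that the fatal-TEAE summary already needs. No other subject's grade changes. LTE SAP 4.3 says the Main Study analysis was complete when that SAP was written. For tables already produced, it is enough to query for any fatal TEAE with blank severity; if there is none, the Grade 5 change alters no result.

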#### 19.1.3. RELATIONSHIP TO STUDY TREATMENT

Relationship is classed as "not related", "unlikely related", "probably related", or "related" (increasing severity of relationship) by the Investigator. A "related" TEAE for the purpose of TEAE summaries is defined as a TEAE with a relationship to study treatment as "related" or "probably related" to study treatment. TEAEs with a missing relationship to study treatment will be regarded as "related" to study treatment. "Unlikely related" will be counted as non-related TEAE. If a subject reports the same AE more than once within the same SOC/PT, the AE with the strictest causality will be used in the corresponding relationship summaries. All TEAEs will be summarized by SOC, PT, and relationship to study treatment.

#### 19.1.4. TEAES LEADING TO DISCONTINUATION OF STUDY TREATMENT

TEAEs leading to permanent discontinuation of study treatment will be identified by action taken being recorded as "Drug withdrawal" on the AE page of the eCRF. All TEAEs leading to discontinuation of study treatment will be summarized by SOC and PT. A listing of all TEAEs leading to discontinuation of study treatment will also be presented.

#### 19.1.5. TEAES LEADING TO STUDY DISCONTINUATION

TEAEs leading to study discontinuation will be noted on the End of Study eCRF. All TEAEs leading to study discontinuation will be summarized by SOC and PT.

#### 19.1.6. SERIOUS AND NON-SERIOUS TEAES

Serious adverse events (SAEs) are those events recorded as "Serious" on the Adverse Events page of the eCRF. All serious TEAEs will be summarized by SOC and PT. All non-serious TEAEs will also be summarized by SOC and PT. A serious AE listing will also be presented.

#### 19.1.7. TEAES LEADING TO DEATH

TEAEs leading to Death are those events which are recorded as "Fatal" on the Adverse Events page of the eCRF. A summary of TEAEs leading to death by SOC and PT will be prepared by treatment.

#### 19.1.8. TEAES OF SPECIAL INTEREST

To date, no AEs of special interest have been identified related to olorinab. Potential AEs of special interest may be identified by clinical or medical reviewers. In addition to appropriate reporting of these events as an AE or SAE, supplementary detailed information may be collected. Any identified AEs of special interest will be summarized by SOC and PT separately. A listing will also be provided.

### 19.1.9. OVERALL SUMMARY OF ADVERSE EVENTS

In addition to the summaries by SOC and PT as described in Sections 19.1.1 to 19.1.5, an overview of TEAEs will be summarized (not broken down by SOC or PT) by number and frequency of subjects and by number of AEs by treatment:

• Any AE (including non-TEAEs)

- Any TEAE
- Any related TEAE
- TEAEs by maximum severity
- Related TEAEs by maximum severity
- TEAEs by relationship to study treatment
- TEAEs leading to death
- Serious TEAEs
- Non-serious TEAEs
- Related Serious TEAEs
- TEAEs leading to study treatment discontinuation
- TEAEs leading to study treatment interruption
- TEAEs leading to study discontinuation
- Related TEAEs leading to study treatment discontinuation
- Related TEAEs leading to study treatment interruption
- Related TEAEs leading to study discontinuation
- TEAE leading to death

### **19.2. DEATHS**

For any reports of death during the study as recorded on the End of Study page of the eCRF, the information will be presented in a listing.

### 19.3. LABORATORY EVALUATIONS

Results from the central laboratory will be included in the reporting of this study for chemistry, hematology, coagulation, urinalysis, thyroid chemistry, celiac, basal metabolic panel, virology, and serum pregnancy. A list of laboratory assessments to be included in the outputs is included in Table 3 in the protocol. If local and central laboratory assessments are available from the same day, central laboratory assessments will be used in the analysis.

Presentations will use SI Units. Quantitative laboratory measurements reported as "< X", i.e. below the lower limit of quantification (BLQ), or "> X", i.e. above the upper limit of quantification (ULQ), will be converted to X for the purpose of quantitative summaries, but will be presented as recorded, i.e. as "< X" or "> X" in the listings.

Laboratory parameters such as hepatic enzymes, renal function and hematology values will be grouped and presented together. The following summaries will be provided for laboratory data:

- Value and change from baseline by visit (for quantitative measurements)
- Incidence of abnormal values according to laboratory reference ranges by visit
- Shift from baseline to end of treatment according to laboratory reference range (for quantitative measurements and categorical measurements)
- Summary of subjects with treatment-emergent abnormal lab results
- Listing of subject's laboratory assessments at all timepoints. Values outside of the central laboratory reference range will be flagged. Values obtained from local laboratory will be flagged.

#### 19.3.1. LABORATORY REFERENCE RANGES AND MARKEDLY ABNORMAL CRITERIA

Quantitative laboratory measurements will be compared with the relevant laboratory reference ranges in SI units and categorized as:

- Low: Below the lower limit of the laboratory reference range.
- Normal: Within the laboratory reference range (upper and lower limit included).
- High: Above the upper limit of the laboratory reference range.
- Treatment-emergent high result: a change from a value less than or equal to the high limit at all baseline visits to a value greater than the high limit at any time during the treatment period.
- Treatment-emergent low result: a change from a value greater than or equal to the low limit at all baseline visits to a value less than the low limit at any time during the treament period.

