# 19.4. 12-LEAD ECG

Results from the central 12-lead ECG Reading Centre will be included in the reporting of this study. The ECGs will be read and interpreted by the central ECG laboratory. For subjects enrolled before protocol amendment 2, there was an over-night observation period following randomization, and ECGs were collected at multiple timepoints on Day 1 and Day 2 (see below).

- Day 1: Prior to the first dose of study treatment and 2, 4, and 8 hours after the first dose (prior to the second dose), and 10 hours after the first dose (2 hours after the second dose).
- Day 2: Prior to the first dose of study treatment, and 2 and 4 hours after the first dose.

At all other indicated visits after baseline, ECGs were collected once per visit, prior to

administration of the first daily dose of study treatment.

For subjects enrolled after protocol amendment 2, on Day 1, ECG was collected prior to the first dose of study treatment and 2 hours after administration of study treatment. At all other indicated visits after baseline, ECGs were collected once per visit, prior to administration of the first daily dose of study treatment.

The following ECG parameters will be reported for this study on the central read for each safety ECG:

- PR Interval (msec)
- QRS Interval (msec)
- QT Interval (msec)
- QTcF Interval (msec) [derived]
- QTcB Interval (msec) [derived, optional]
- Heart Rate (HR) (bpm)
- Overall interpretation of ECG (Investigator's judgment):
  - Normal
  - Abnormal, Not Clinically Significant (Abnormal NCS)
  - Abnormal, Clinically Significant (Abnormal CS)

The following summaries will be provided by treatment group for ECG data:

- Value and change from baseline by visit (for quantitative measurements)
- Shift in normal/abnormal NCS/abnormal CS from baseline to worst investigator overall interpretation of clinical significance post-baseline
- Shift in markedly abnormal categories from baseline to post-baseline by visit

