### 18.3. LABORATORY EVALUATIONS

Results from the central laboratory will be included in the reporting of this study for chemistry, hematology, coagulation, urinalysis, thyroid chemistry, celiac, and virology. pregnancy. A list of laboratory assessments to be included in the outputs is included in Table 3 in the protocol. If local and central laboratory assessments are available from the same day, central laboratory assessments will be used in the analysis.

Presentations will use SI Units. Quantitative laboratory measurements reported as "< X", i.e. below the lower limit of quantification (BLQ), or "> X", i.e. above the upper limit of quantification (ULQ), will be converted to X for the purpose of quantitative summaries, but will be presented as recorded, i.e. as "< X" or "> X" in the listings.

Laboratory parameters such as hepatic enzymes, renal function and hematology values will be grouped and presented together. The following summaries will be provided for laboratory data:

- Value and change from LTE baseline by visit (for quantitative measurements)
- Incidence of abnormal values according to laboratory reference ranges by visit
- Shift from LTE baseline to end of treatment according to laboratory reference range (for quantitative measurements and categorical measurements)
- Summary of subjects with treatment-emergent abnormal lab results
- Listing of subject's laboratory assessments at all timepoints. Values outside of the central laboratory reference range will be flagged. Values obtained from local laboratory will be flagged.

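### The planned laboratory tables do not count subjects who worsen from an already abnormal baseline, and the end-of-treatment shift can show such a subject as improved

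*SAP*

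**What the plan says.** Main Study SAP 19.3.1 sorts quantitative laboratory values into low, normal and high against the reference range. It then defines "Treatment-emergent high result: a change from a value less than or equal to the high limit at all baseline visits". The on-treatment half of that definition reads "to a value greater than the high limit at any time during the treatment period". The mirror definition begins "Treatment-emergent low result: a change from a value greater than or equal to the low limit at all baseline visits". The visible text does not say which visits are baseline visits.

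SAP 19.3 lists the laboratory outputs:
- values and changes at each visit;
- the frequency of out-of-range values at each visit;
- a shift table, worded as "Shift from baseline to end of treatment according to laboratory reference range";
- a count of subjects with treatment-emergent abnormal results;
- a listing that flags out-of-range values.

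LTE SAP 18.3.1 repeats the definitions, and LTE SAP 18.3 has the matching shift, "Shift from LTE baseline to end of treatment according to laboratory reference range".

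Protocol 8.3.1.1 places clinically relevant laboratory changes within the primary safety endpoint of the Main Study, and the synopsis does the same for the LTE. Protocol 8.3.4.3 requires shift tables but fixes no time point for them.

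**The concern.** The treatment-emergent count is conditional on an in-range baseline. A subject outside a limit at any baseline visit can never enter the count in that direction, however far the value later moves. The shift table might have caught this subject, but it looks only at the last on-treatment category. A marked rise that resolves before the end of treatment leaves no trace there and, from a high baseline, reads as an improvement.

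The same SAP treats its other safety data differently:
- Adverse events (19.1): a pre-existing event that becomes more severe on treatment counts as treatment-emergent.
- ECG interpretation (19.4): the shift runs "from baseline to worst investigator overall interpretation of clinical significance post-baseline".
- ECG intervals (19.4.1): outliers are defined by size and by change from baseline.
- Blood pressure (19.5, Table 2): the criteria combine a threshold with a change from baseline.

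At stake is whether a dose-related laboratory signal in subjects with mildly abnormal baselines would be counted by subject in a table. Otherwise the reader has to assemble it from several outputs.

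**Working it through.** The documents give no figure to reproduce for this point. The check applies the two rules as written to assumed profiles, in multiples of the upper limit of normal (ULN).

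**Rules**
- Treatment-emergent high = every baseline value ≤ 1 and at least one on-treatment value > 1 (SAP 19.3.1).
- Planned shift = category of the last baseline value → category at end of treatment (SAP 7.2 and 19.3).
- Alternative shift = category of the last baseline value → category of the highest on-treatment value.

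**Assumed values.** The visits are the post-baseline treatment visits in SAP 9.1. The visible text does not show that laboratory samples are taken at each one, so this is an assumption.

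| Profile | Screening, Day 1 | Weeks 2, 4, 8, 10, 12 |
|---|---|---|
| A | 1.2, 1.2 | 1.3, 8, 2, 1.1, 0.9 |
| B | 1.2, 1.2 | 1.3, 8, 8, 8, 8 |
| C | 0.95, 0.98 | 1.01, 0.9, 0.9, 0.9, 0.9 |
| D | 1.1, 0.9 | 1.3, 8, 2, 1.1, 0.9 |
| E | 0.9, 0.9 | 1.3, 8, 2, 1.1, 0.9 |

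**Results**

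| Profile | Treatment-emergent high | Planned shift | Worst-value shift | Visits counted High in by-visit incidence |
|---|---|---|---|---|
| A | No | High → Normal | High → High | Weeks 2, 4, 8, 10 |
| B | No | High → High | High → High | all five |
| C | Yes | Normal → Normal | Normal → High | Week 2 |
| D | No, if Screening is a baseline visit; otherwise Yes | Normal → Normal | Normal → High | Weeks 2, 4, 8, 10 |
| E | Yes | Normal → Normal | Normal → High | Weeks 2, 4, 8, 10 |

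**Reading the tables**
1. C, a crossing of 1%, is counted. A and B, which rise from 1.2 to 8 (8 / 1.2 = 6.7-fold), are not.
2. E shows that a transient peak from an in-range baseline is counted. The gap is confined to subjects out of range at a baseline visit.
3. D turns on an undefined term. The same data give Yes or No depending on which visits are treated as baseline.
4. A worst-value shift alone removes the false improvement in A, but A and B then read High → High because there is only one High category. Any cut-point between 1.2 and 8 times the limit would move A and B up a category and also separate C from E.

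**How many subjects.** The documents do not give the share of subjects with an out-of-range baseline. If that share is q for a given analyte and direction, then q × 60 per arm and q × 240 overall can never be counted:
- q = 2%: 0.02 × 60 = 1.2 per arm; 0.02 × 240 = 4.8 overall.
- q = 20%: 0.20 × 60 = 12 per arm; 0.20 × 240 = 48 overall.

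The range for q is an assumption. These figures are subjects barred from the count, not subjects whose worsening is missed. The latter also depends on how many of them worsen, which is unknown.

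**The case against.** The strongest reply is that the excursion shows elsewhere, and much of this stands. The by-visit incidence in SAP 19.3 has no baseline condition, so profile A is counted High at four visits. Protocol 8.3 includes the maximum in continuous summaries, so an 8-fold value at a scheduled visit would be the arm's maximum unless another subject is higher. SAP 7.3 brings all measurements into summaries of abnormalities. Protocol 7.8.1.1 includes clinically relevant laboratory changes among possible adverse events, and these are graded by CTCAE v5.0. A DSMB also reviews aggregate safety data.

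Each route has a limit. By-visit incidence gives 1.1 and 8 times the limit equal weight and ignores baseline. A maximum gives no subject count, and the windowing in SAP 7.4 can drop an unscheduled peak from the by-visit values. Recording laboratory worsening as an adverse event is left to the Investigator (Protocol 7.7.4).

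Four stronger readings are tempting but unsupported:
- A reader might infer that only a first crossing counts, or that any peak resolving before Week 12 is lost. The rule covers the whole treatment period, and profile E is counted.
- A reader might infer that such a signal would surface only in listings or diluted means. The by-visit incidence and maxima contradict that.
- A reader might see a contradiction with the baseline definition in SAP 7.2. That definition is a default, and 19.3.1 may depart from it. What remains is that 19.3.1 does not say which visits it means.
- A reader might conclude from the heading "LABORATORY REFERENCE RANGES AND MARKEDLY ABNORMAL CRITERIA", with no such criteria in the visible text, that the plan has none. The public copy has removed pages and the table shells are separate, so this cannot be concluded. What can be said is that no laboratory summary listed in 19.3 refers to such criteria.

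Restricting the term to subjects in range before treatment is a coherent definition, and the SAP does comply with Protocol 8.3.4.3. For the LTE the practical gain is smaller: it was ended early and is summarized descriptively (LTE SAP 4.3 and 8.1).

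**Conclusion.** The point holds in a limited form. In both SAPs, a subject outside a limit at baseline who worsens markedly and recovers is absent from the treatment-emergent count and can read High-to-Normal in the shift table. Other outputs can show the excursion. None of the listed laboratory summaries counts subjects who worsened from an abnormal baseline, and none grades the size of an excursion.

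This follows from the wording alone. The profiles only illustrate it, and the result for profile D also assumes that Screening is a baseline visit. Abnormal baselines are possible, since Protocol 4.5 lets some out-of-threshold results before randomization stand on the Investigator's judgment, but their frequency is not stated. The number of subjects affected is therefore unknown. This is an inexpensive improvement to a primary safety summary; it does not show that a signal would be missed.

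**What to change.** Keep all planned laboratory tables. In SAP 19.3 and 19.3.1, and in LTE SAP 18.3 and 18.3.1:
1. Add a shift from the 7.2 baseline to the worst post-baseline value, using all measurements as in 7.3, in prespecified size categories. These could be CTCAE v5.0 grades where they exist (already the adverse-event scale) or multiples of the reference limit.
2. Count as treatment-emergent any on-treatment worsening to a higher category than the 7.2 baseline, including from an abnormal baseline.
3. State which visits count as baseline visits, or replace that condition with the 7.2 baseline.

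Items 1 and 2 belong together, because a worst-value shift with a single High category leaves profiles A and B unchanged in appearance. The cost is some SAP wording and a few extra tables from data already collected. No new samples are needed, and the protocol need not change. LTE SAP 4.3 indicates that the Main Study analysis was complete when that plan was written. For the Main Study, tables added after that would be reported as unplanned analyses under SAP 5.2.
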